7.3.6.3 Nemolizumab Cohort

The Nemolizumab Cohort will include all pregnancies among women with moderate to severe AD or PN and at least one dispensing or dose of nemolizumab from 95 days (approximately 14 weeks) prior to ECD through the end of pregnancy. Cohort entry will be set at the date of the first nemolizumab dispensing, rounded down to the nearest week of gestation.

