7.3.6 Study Population

7.3.6.1 Exposure Cohorts and Cohort Entry

[figure not shown]
Based on the sequential cohort design, a series of study cohorts will be established for each gestational week of pregnancy ([Caniglia et al., 2023](#); [Hernández-Diaz S et al., 2023](#)). To ensure capture of exposure to AD/PN treatments prior to the ECD but which remain in the body at ECD, the first gestational week of pregnancy will be extended (prior to ECD) by 5 times the half-life for each AD/PN treatment. For example, since nemolizumab has a half-life of 18.9 days ([Nemluvio PI, 2025](#)), the first gestational week for nemolizumab will begin 95 days (approximately 14 weeks) prior to ECD. The half-life for each AD/PN treatment is provided in [Appendix D](#).

As nemolizumab and the comparator AD/PN treatments are injection drugs that are dispensed at a pharmacy for self-injection, treatment duration will be defined as date of dispensing plus 5 times the half-life of the therapy when a single pre-filled syringe, pen, or autoinjector is dispensed. When multiple units are dispensed, the days' supply will be calculated based on the quantity dispensed and recommended administration schedule; treatment duration will be calculated as the date of dispensing plus the days' supply plus 5 times the half-life of the therapy. A treatment will be considered to be overlapping with the first gestational week of pregnancy if there is at least one dispensing or dose received during the period 5 times the half-life prior to ECD through the end of the first gestational week. At each gestational week, we will first restrict to eligible pregnancies with no administrations or dispensings of nemolizumab or the other AD/PN treatments from 5 times the half-life of the corresponding treatment (e.g., 95 days, or approximately 14 weeks, for nemolizumab) before ECD through the end of the prior gestational week. We will then classify exposure status as exposed to nemolizumab, exposed to other AD/PN treatments, or unexposed based on the pregnancy's receipt of nemolizumab or other AD/PN treatments during that gestational week. Pregnancies among women with claims for both nemolizumab and another AD/PN treatment during the relevant exposure window will be excluded. For exposed pregnancies with more than one dose of the index treatment (e.g., two doses of nemolizumab) during pregnancy, cohort entry will align with the first dose.

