7.3.6.2 Etiologically Relevant Windows for Exposure Assessment

For most study outcomes, the analysis will include weekly exposure cohorts that are formed throughout pregnancy (i.e., approximately 40 potential weekly cohorts beginning at Week 2 through Week 40 or the latest observed week of gestation). However, analyses of spontaneous abortion and elective termination will be restricted to the Week 2-19 Cohorts, because spontaneous abortion is defined as a pregnancy loss occurring before 20 weeks' gestation, and all pregnancies that are ongoing at Week 20 will be censored in these analyses. Analyses of preterm birth will be restricted to Weeks 2-36 Cohorts, because preterm birth is defined as a livebirth occurring before 37 weeks' gestation, and analyses of ectopic pregnancy and MCMs will be restricted to Weeks 2-13 Cohorts.

Table 2 depicts the potential gestational weeks of cohort entry for each study outcome relative to the timing of outcome assessment.

Table 2 Etiologically relevant exposure windows for study outcomes

Study Outcome	Etiologically Relevant Exposure Window	Potential Cohort Entry of Pregnancy	Start of Follow-up¹	Censoring Events²
Ectopic pregnancy	First trimester	Week 2 – Week 13	Cohort entry	End of pregnancy, disenrollment from the health plan/8 weeks of no clinical activity, or the end of the study period
Elective termination	ECD through 19 weeks' gestation (19 weeks + 6 days)	Week 2 – Week 19	Cohort entry	20 weeks + 0 days, end of pregnancy, disenrollment from the health plan/8 weeks of no clinical activity, or the end of the study period
Live births	Entire pregnancy	Week 2 – Week 40	Later of cohort entry or 20 weeks + 0 days	End of pregnancy, disenrollment from the health plan/8 weeks of no clinical activity, or the end of the study period
Preterm birth	ECD through 36 weeks' gestation (36 weeks + 6 days)	Week 2 – Week 36	Later of cohort entry or 20 weeks + 0 days	37 weeks + 0 days, end of pregnancy, disenrollment from the health plan/8 weeks of no clinical activity, or the end of the study period

Study Outcome	Etiologically Relevant Exposure Window	Potential Cohort Entry of Pregnancy	Start of Follow-up ¹	Censoring Events ²
Spontaneous abortion	ECD through 19 weeks' gestation (19 weeks + 6 days)	Week 2 – Week 19	Cohort entry	20 weeks + 0 days, end of pregnancy, disenrollment from the health plan/8 weeks of no clinical activity, or the end of the study period

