7.3.6.4 Other AD/PN Treatment Cohort

The Other AD/PN Treatment Cohort will include all pregnancies among women with moderate to severe AD or PN and at least one dispensing/administration or dose of selected other AD or PN treatments from 5 times the half-life of the medication prior to ECD through the end of pregnancy. The cohort entry date will be set at the date of the first comparator treatment dispensing/administration, rounded down to the nearest week of gestation.

The following comparator treatments will define this cohort:

- Dupilumab (indicated for both moderate to severe AD and PN)
- Lebrikizumab (indicated for moderate to severe AD only)
- Tralokinumab (indicated for moderate to severe AD only)

These therapies are proposed because they are typically used in patients with moderate to severe AD or PN, similar to the expected population of patients using nemolizumab.

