7.4.3.5 AD and PN History and Treatment

Covariates related to AD and PN history and treatment will be using all available data prior to the cohort entry (up to 5 years). The AD therapies include treatments that are for mild AD and are not included in the moderate to severe AD algorithm.

- AD
 - Number of AD diagnoses on unique days
- PN
 - Number of PN diagnoses on unique days
- Treatments for AD and/or PN
 - Abrocitinib
 - Dupilumab
 - Lebrikizumab
 - Tralokinumab
 - Upadacitinib
 - Baricitinib
 - Topical Tacrolimus
 - Crisaborole
 - Oral and parental corticosteroids
 - Phototherapy
 - Systemic immunosuppressants
 - Cyclosporine
 - Azathioprine
 - Methotrexate
 - Mycophenolate
 - Belimumab
 - Leflunomide
 - Interferon gamma
 - Rituximab

- Topical corticosteroids
 - High potency
 - Medium potency
 - Low potency
- Topical calcineurin inhibitors
- Topical tacrolimus, pimecrolimus
- Gabapentinoids (gabapentin, pregabalin)
- Cannabinoids
- Antidepressants (serotonin and norepinephrine reuptake inhibitors, selective serotonin reuptake inhibitors, or tricyclic antidepressants)
- Topical ketamine/amitriptyline/lidocaine
- Topical calcipotriol

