7.7.3.1 Propensity Score and IPTW

In the final study report, comparative analyses will be performed incorporating stabilized IPTW to adjust for potential confounding. The stabilized IPTW will be appropriately defined such that the causal estimate is the average treatment effect in the treated (ATT; [Austin and Stuart, 2015](#)). Briefly, to estimate the ATT, the weights are defined such that every nemolizumab-exposed pregnancy receives a weight of 1, while the comparator pregnancies receive weights that are a function of the propensity score. Each pregnancy's propensity score (the probability of receiving nemolizumab versus a comparator or no treatment, given membership in the study population and a set of covariates) will be estimated using a logistic regression model with exposure status as the outcome (dependent variable). A total of 2 propensity score models will be generated: one for the comparison of the Nemolizumab Cohort versus Other AD/PN Treatment Cohort and another for the comparison of the Nemolizumab Cohort versus the Unexposed Cohort. The covariates listed in [Section 7.4.3](#) (excluding Sections 7.4.3.6 and 7.4.3.7) will be considered for inclusion in the model as independent (predictor) variables. The propensity score model will only include covariate information from cohort entry or earlier. In addition to the pre-specified variables in [Section 7.4.3](#), the most common diagnoses, procedures, and medications observed prior to ECD will be evaluated to ensure no important confounders are missed.

If there are too many variables given the number of pregnancies exposed to nemolizumab (e.g., < 10 exposed pregnancies for every variable in the propensity score model), the number of variables may be reduced. For variable pairs that are highly correlated (e.g., correlation coefficient > 0.9), one may be eliminated.

Balance between the cohorts will be evaluated before and after weighting. Variables with an absolute standardized difference < 0.1 will be considered balanced. If a variable has an absolute standardized difference ≥ 0.1 , the imbalanced covariate will be included in the outcome model. Overall balance between the cohorts, both before and after weighting, will be assessed via overlap (or lack thereof) in histograms of the propensity score. The distribution of weights will also be inspected. To address the impact of large weights on the analysis, truncation of weights greater than 10 will be considered.

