11.4 Appendix D: Half-lives for Cohort Defining Treatments

Drug	Half-life	5 times half-life*	1.5 times half-life (sensitivity)*	3 times half-life (sensitivity)*
Dupilumab	2 weeks	10 weeks	3 weeks	6 weeks
Lebrikizumab	24.5 days	123 days	37 days	74 days
Nemolizumab	18.9 days	95 days (approximately 14 weeks)	29 days	57 days
Tralokinumab	3 weeks	15 weeks	32 days	9 weeks

*Numbers were rounded up to the nearest whole day.

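### Cohort entry for fills before conception is dated in conflicting ways, and at Week 2 + 0 days the comparator's index fill becomes a baseline covariate

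*Protocol*

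**What the plan says.** The cohort sections date entry by the fill. Section 7.3.6.3 states "Cohort entry will be set at the date of the first nemolizumab dispensing, rounded down to the nearest week of gestation" and section 7.3.6.4 states "The cohort entry date will be set at the date of the first comparator treatment dispensing/administration, rounded down to the nearest week of gestation". Section 7.3.6.1 repeats the rule. Both cohorts admit fills from five half-lives before ECD.

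The design sections date entry by the weekly cohort. Section 7.3.6.1 says that "the first gestational week for nemolizumab will begin 95 days (approximately 14 weeks) prior to ECD". Section 7.3.6.2 counts "approximately 40 potential weekly cohorts beginning at Week 2 through Week 40", and adds that "analyses of ectopic pregnancy and MCMs will be restricted to Weeks 2-13 Cohorts". Table 2 lists no potential entry before Week 2 for any outcome. The only worked example is Week 8, where entry is 8 weeks + 0 days. There is none for a preconception fill.

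On covariates, section 7.4.3.5 says "Covariates related to AD and PN history and treatment will be using all available data prior to the cohort entry (up to 5 years". Its list includes dupilumab, lebrikizumab and tralokinumab, but not nemolizumab. Section 7.7.3.1 makes the listed covariates candidates for the propensity model, limits them only to information from cohort entry or earlier, and says of any that stay unbalanced that "the imbalanced covariate will be included in the outcome model".

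**The concern.** Cohort entry anchors the six-month enrollment requirement (7.3.2), the baseline period (7.3.6.6), the start of follow-up (7.3.6.7, Table 2), the covariate look-back (7.4.3) and the matching (7.7.3). Section 7.8.1 expects each research partner to follow a common protocol. Two programmers working from this text could date the same preconception fill differently and build different cohorts.

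The date also decides whether the comparator's own index fill counts as history. If it does, the contrast with the Other AD/PN Treatment Cohort, including the primary analysis of major congenital malformations (MCMs), may adjust for part of the exposure it is meant to measure.

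**Working it through.** **Windows.** Half-lives are from Appendix D (for example "Dupilumab 2 weeks 10 weeks 3 weeks 6 weeks"). The window is 5 × half-life, rounded up to a whole day.

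- Nemolizumab: 5 × 18.9 = 94.5, so 95 days
- Dupilumab: 5 × 14 = 70 days
- Tralokinumab: 5 × 21 = 105 days
- Lebrikizumab: 5 × 24.5 = 122.5, so 123 days

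All four agree with Appendix D. The windows themselves are not in question.

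**What rounding down gives.** Table 1 sets ECD at LMP + 14 days. A fill d days before ECD is in gestational week floor((14 − d)/7).

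- Nemolizumab, d = 95: floor(−81/7) = −12
- Any drug, d = 1: floor(13/7) = 1

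Preconception nemolizumab fills therefore lie in weeks −12 to 1. None of these is a Table 2 entry week. Rounding down cannot carry a preconception fill forward to Week 2, so the two sets of sections cannot both be followed literally.

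**Reading 1: entry at 2 weeks + 0 days (the ECD).** A preconception index fill precedes entry by 1 to 70 days for dupilumab, 1 to 105 for tralokinumab and 1 to 123 for lebrikizumab. It is therefore inside the look-back. Every active-comparator pregnancy that enters on such a fill is a yes on at least one of the three drug covariates by construction. A nemolizumab pregnancy can be a yes only through use before the exposure window, because section 7.3.3.2 excludes dual exposure within it. The covariate thus partly encodes treatment group, and nothing in 7.4.3.5 or 7.7.3.1 removes the index fill. The contrast with the Unexposed Cohort does not have this problem, since that cohort has no index fill.

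**Reading 2: entry at the fill date.** The covariate problem goes away. Table 2 starts follow-up at cohort entry for ectopic pregnancy, elective termination and spontaneous abortion, so it would start before conception, when none of these can occur.

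**Reading 3: entry at the start of the extended week.** The covariate problem again goes away, but entry is 95, 70, 105 or 123 days before ECD by drug. Against nemolizumab, dupilumab starts 95 − 70 = 25 days later, tralokinumab 105 − 95 = 10 days earlier and lebrikizumab 123 − 95 = 28 days earlier. The sequential design is meant to align these starts.

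**Matching.** Only if preconception fills were matched in separate weekly bins would a further gap appear. Dupilumab's earliest bin is floor((14 − 70)/7) = −8. Nemolizumab fills 71 to 95 days before ECD (weeks −12 to −9) would then have no dupilumab counterpart. That is 25 of 95 preconception days, or 26%.

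**The case against.** The strongest reply is that section 7.3.6.1 already resolves the matter. All preconception fills fall in one drug-specific first week, Table 1 starts the first trimester and the pregnancy period at the same point, and rounding down would then mean the start of that week. The protocol never creates negative weekly bins, and Week 2 + 0 days is nowhere stated for these fills. The listed covariates are only considered for the model, section 7.3.6.6 allows other assessment windows, and leaving out an index fill could be an operational detail for the SAP. The first sensitivity analysis in 7.7.3.5.4 uses only dispensings after ECD and avoids the issue.

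Much of this stands. Reading 3 is tenable and escapes the covariate problem, but it conflicts with Table 2's entry weeks and gives each drug its own start of follow-up. The sensitivity analysis does not repair the main analysis. An SAP can add detail, but it needs one protocol date to follow.

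A reader might infer more than the documents support:

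- **That exposed pregnancies would be lost for want of a comparator.** The 25-day gap depends on bins the protocol does not define. Even then, tralokinumab and lebrikizumab cover those days for atopic dermatitis (AD). Only prurigo nodularis (PN) would have no indicated active comparator. Section 7.3.6.1 also counts a dose received in the window, which may soften the gap.
- **That the imbalance can be quantified.** If 20%, 40% or 60% of nemolizumab users had earlier use of another biologic, (1 − p)/√(p(1 − p)/2) gives a standardized difference of 2.83, 1.73 or 1.15. Those shares are assumed. The covariate is a composite the protocol does not list, and the figure applies to the preconception subset, whereas the 0.1 limit is for whole cohorts.
- **That follow-up for the primary outcome starts before conception.** Table 2 starts MCM and small-for-gestational-age follow-up at delivery, and live birth, preterm birth and stillbirth no earlier than 20 weeks.

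**Conclusion.** The conflict is real and should be corrected. The protocol gives incompatible entry dates for fills before ECD, and each available reading has a cost. Week 2 + 0 days lets the comparator's index fill count as baseline history. The fill date starts follow-up before conception for three outcomes. The start of the extended week does that too, at a different time for each drug.

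In days, the size is as shown above: entry up to 95 days before ECD for nemolizumab, and starts that differ by drug from 70 to 123 days under Reading 3. The effect on the estimates cannot be sized, because the protocol does not say how many pregnancies will enter on a preconception fill or how common earlier biologic use is. The covariate consequence assumes Week 2 + 0 entry and that the drug-history covariates are retained; the text leaves both open. The follow-up consequence for elective termination and spontaneous abortion assumes that the extended first week applies to them. Section 7.3.6.1 says so without exception, although Table 2 words their exposure window as opening at ECD.

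**What to change.** - **Entry (7.3.6.1, 7.3.6.3 to 7.3.6.5).** For every pregnancy whose qualifying fill precedes ECD, and for its matched unexposed pregnancies, set cohort entry and start of follow-up at 2 weeks + 0 days in all cohorts.
- **Matching.** Treat the whole extended window as one gestational week (Week 2), with calendar week taken at ECD.
- **Biologic history (7.4.3.5).** Exclude the index drug's dispensings within the exposure window from the covariates for the cohort-defining biologics, for example by defining the covariate as prior use of a biologic other than the index drug.
- **All other covariates.** Keep one common look-back in all cohorts. Ending the whole treatment look-back at each drug's own window would measure steroid and immunosuppressant history over different periods by cohort.

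The cost is wording, plus slightly less information on recent biologic history. No new data are needed. The 183-day baseline counted back from ECD still covers the longest window (123 days).

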7.3.6.4 Other AD/PN Treatment Cohort

The Other AD/PN Treatment Cohort will include all pregnancies among women with moderate to severe AD or PN and at least one dispensing/administration or dose of selected other AD or PN treatments from 5 times the half-life of the medication prior to ECD through the end of pregnancy. The cohort entry date will be set at the date of the first comparator treatment dispensing/administration, rounded down to the nearest week of gestation.

The following comparator treatments will define this cohort:

- Dupilumab (indicated for both moderate to severe AD and PN)
- Lebrikizumab (indicated for moderate to severe AD only)
- Tralokinumab (indicated for moderate to severe AD only)

These therapies are proposed because they are typically used in patients with moderate to severe AD or PN, similar to the expected population of patients using nemolizumab.

7.3.6.5 Unexposed Cohort

The Unexposed Cohort will include all pregnancies among women with moderate to severe AD or PN who have no dispensings or administrations of nemolizumab or the other monoclonal antibody treatments used to defined the Other AD/PN Treatment Cohort (i.e., dupilumab, lebrikizumab, tralokinumab) from 5 times the half-life of each medication prior to ECD through the end of pregnancy. The cohort entry date will be matched to the date of nemolizumab dispensing, rounded down to the nearest week of gestation.

This cohort may include pregnancies among women who have dispensings or administrations of other treatments indicated for moderate to severe AD or PN (e.g., immunosuppressants, corticosteroids). Exposure to other treatments for moderate to severe AD or PN will be measured and adjustment for or stratification by use of these treatments may be considered during the analysis.

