7. RESEARCH METHODS

7.1 Study Design

This will be an observational cohort study that will use multiple existing databases to assess pregnancy and infant outcomes among patients with moderate to severe AD or PN. Among patients with moderate to severe AD or PN, pregnancies that begin (based on the ECD) between 12 August 2024 and 31 March 2032 (or latest data available) will be identified. This study will assess pregnancy and infant outcomes among pregnancies from patients within 3 cohorts:

- Nemolizumab Cohort: pregnancies among patients with moderate to severe AD or PN exposed to nemolizumab during pregnancy;
- Other AD/PN Treatment Cohort: pregnancies among patients with moderate to severe AD or PN exposed to other AD or PN treatments, including monoclonal antibodies other than nemolizumab, during pregnancy; and
- Unexposed Cohort: pregnancies among patients with moderate to severe AD or PN who are not exposed to nemolizumab or any of the comparator AD or PN treatments during pregnancy.

The subset of women whose pregnancy outcomes are live births will be linked to their infants to extend infant follow-up for up to one year. Maternal exposure to nemolizumab, as well as diagnoses of moderate to severe AD and PN, will be identified. All qualifying pregnancies per woman will be included in the study. The cohorts of women will be followed through the end of pregnancy to assess pregnancy outcomes of ectopic pregnancy, elective terminations, live births, preterm birth, spontaneous abortion, and stillbirth, with infant follow-up for up to one year after birth to assess the occurrence of infant outcomes of MCMs (primary outcome) and SGA birth.

During the monitoring phase, the accrual of nemolizumab-exposed pregnancies and live births in the Optum Research Database (ORD) will be reported in the Periodic Safety Update Reports (PSURs). As additional data sources will be needed to achieve an adequate sample size for the study of rare pregnancy and infant outcomes, Optum's Market Clarity Data (linked claims-electronic health record [EHR] database) and a feasibility assessment of the potential data sources under consideration will be included in the 2029 PSUR. To allow time for uptake of nemolizumab, accrual of nemolizumab-exposed pregnancies and live births in all selected databases will be reported in the PSURs beginning at the midpoint of the study (2030).

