For the final report, pregnancies exposed to nemolizumab and their matched comparators will be identified in the selected databases. The final report analyses will employ a target trial emulation approach using a sequential matched cohort design that aligns cohort entry by gestational week (Caniglia et al., 2023; Hernández-Díaz et al., 2023). Nemolizumab-exposed pregnancies will be 1:4 matched to comparator pregnancies based on maternal age at cohort entry, gestational week of dispensing, indication, and calendar week. The frequency of pregnancy and infant outcomes among nemolizumab-exposed pregnancies and comparator pregnancies will be calculated. In the comparative analysis, pregnancies among patients with moderate to severe AD or PN who were

exposed to nemolizumab will be contrasted with the comparator groups using stabilized inverse probability of treatment weighting (IPTW) to adjust for potential confounding. RRs will be estimated using robust Poisson regression models and HRs using Cox proportional hazards models.

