7.3.3.2 Concurrent Exposure to Nemolizumab and Other AD/PN Treatments

Pregnancies among women with claims for both nemolizumab and another AD/PN Treatment during the relevant exposure window will be excluded.

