Cohort entry will be set at the date of dispensing in the Nemolizumab Cohort (i.e., the earliest nemolizumab administration date during a pregnancy) and the Other AD/PN Treatment Cohort,

and the corresponding day of gestation among unexposed pregnancies, rounded down to the nearest week. For example, for pregnancies entering the Week 8 Cohort, we will first select all pregnancies with no nemolizumab or other AD/PN treatment from 5 times the half-life before ECD through 7 weeks' + 6 days' gestation. Then, we will assign the pregnancies that receive nemolizumab during Week 8 (8 weeks + 0 days through 8 weeks + 6 days) to the nemolizumab-exposed group, those that received another AD/PN treatment to the other treatment-exposed group, and those that did not receive nemolizumab or another AD/PN treatment during Week 8 to the unexposed group. Cohort entry among the Week 8 nemolizumab and comparator cohorts will be set to 8 weeks' + 0 days. The pregnancies in the Week 8 exposed cohort will no longer be eligible for inclusion in subsequent weekly cohorts. However, the pregnancies in the Week 8 unexposed group will go on to be eligible for inclusion in the Week 9 Cohort, at which point their exposure status would be reassessed during Week 9 (9 weeks + 0 days through 9 weeks + 6 days). A pictorial depiction of this process can be found in Figure 1 and key pregnancy dates can be found in Table 1. If the study size does not permit weekly sequential cohorts, the cohorts may be collapsed into longer (e.g., 2-week, 4-week) intervals as needed.

Figure 1 Sequential cohort design, depicting an example of cohort entry for the Week 7 and Week 8 cohorts

Abbreviations: AD, atopic dermatitis; ECD, estimated conception date; PN, prurigo nodularis

Table 1 Pregnancy dates

Date	Definition
LMP	First day of last menstrual period 0 gestational weeks ^{0/7 days}
Gestational age	Weeks of gestation Anchored by LMP Number of completed weeks elapsed after LMP

Date	Definition
ECD	Estimated as LMP + 14 days 2 gestational weeks ^{0/7 days}
First trimester	Begins at ECD minus 5 times the half-life of the treatment Ends at LMP + 97 days
Second trimester	Begins at LMP + 98 days Ends at LMP + 195 days
Third trimester	Begins at LMP + 196 days Ends at pregnancy outcome
Pregnancy period	Begins at ECD minus 5 times the half-life of the treatment Ends at pregnancy outcome

Abbreviations: ECD, estimated conception date; LMP, first day of last menstrual period

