7.7.3.5.4 Alternative Exposure Definition to Assess Exposure Misclassification

To assess potential exposure misclassification, we will perform four sensitivity analyses on the association between nemolizumab use and the study outcomes. First, exposure to nemolizumab and the other AD/PN treatments will be defined by dispensings/administrations during pregnancy (i.e., after ECD) only. Additionally, an analysis in which exposure is defined as the presence of 2 or more dispensings/administrations [to assess possible stockpiling] will be conducted. This dispensing-based sensitivity analysis may be more robust to potential misclassification of the exposure period, particularly for treatments with long half-lives. There will also be two exposure misclassification sensitivity analyses that change the beginning of the exposure window to 3 times and 1.5 times the half-life of the relevant treatment, respectively. The definitions of these windows can be found in [Appendix D](#).

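### The Unexposed Cohort is defined by non-use to the end of pregnancy, which contradicts the weekly sequential rule and, if applied, biases the unexposed contrast for early loss

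*Protocol*

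**What the plan says.** Section 7.1 adopts a target-trial approach with a "sequential matched cohort design that aligns cohort entry by gestational week". Section 7.3.6.1 gives the operating rule. At each gestational week, a pregnancy is eligible if it has had no study biologic from five half-lives "before ECD through the end of the prior gestational week". The worked Week 8 example then assigns "those that did not receive nemolizumab or another AD/PN treatment during Week 8 to the unexposed group", and adds that "the pregnancies in the Week 8 unexposed group will go on to be eligible for inclusion in the Week 9 Cohort", where exposure is assessed again.

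Section 7.3.6.5, which defines the Unexposed Cohort, requires no nemolizumab, dupilumab, lebrikizumab or tralokinumab "from 5 times the half-life of each medication prior to ECD through the end of pregnancy". The cohort bullet in 7.1 agrees with it: "not exposed to nemolizumab or any of the comparator AD or PN treatments during pregnancy".

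Two other rules may also use later treatment. Section 7.3.3.2 states: "Pregnancies among women with claims for both nemolizumab and another AD/PN Treatment during the relevant exposure window will be excluded". Section 7.7.3.5.4 plans "an analysis in which exposure is defined as the presence of 2 or more dispensings/administrations". Neither says that only claims up to cohort entry count.

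**The concern.** A pregnancy untreated through Week 8 that starts a biologic in Week 9 belongs to the Week 8 unexposed group under 7.3.6.1 and is barred from the Unexposed Cohort under 7.3.6.5. Table 2 and 7.3.6.7 list no censoring at a later treatment start, so the exclusion cannot be read as censoring in other words.

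The whole-pregnancy rule conditions on the future. A pregnancy lost at nine weeks has no time left to start a biologic and stays in the comparator, while one that continues and starts later is taken out. The comparator is thereby enriched for early losses, which is the kind of immortal-time problem that week-by-week alignment is meant to avoid. Taken alone, this mechanism errs towards reassurance in a safety study, and a larger sample does not remove it.

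Under 7.8.1 each partner site works from the common protocol and SAP, and 7.7.3.4 combines the site estimates. On the present text, sites could build different comparators.

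**Working it through.** **The plan's own figure.** Table 3 (7.5) asks for 77, 37 and 22 exposed pregnancies for spontaneous abortion at RR 2, 2.5 and 3, with 14% risk, 1:4 allocation, 80% power and two-sided 0.05. The Fleiss formula without continuity correction returns 77, 37 and 22. For RR 2:

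- p1 = 0.28, p0 = 0.14, pooled p = (0.28 + 4 × 0.14)/5 = 0.168.
- n = [1.96·√(1.25 × 0.168 × 0.832) + 0.842·√(0.28 × 0.72 + 0.14 × 0.86/4)]² / 0.14² ≈ 76.5, rounded up to 77.

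The 14% is therefore the planning risk. The sample sizes are not affected by this point.

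**Inputs for the bias.**

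- Risk of spontaneous abortion: 14% (Table 3).
- True effect: none (RR = 1).
- f, the share of unexposed pregnancies that would start a study biologic later if they continued: not given in the protocol, so assumed.
- Rough scale for f: Table 4 shows 209 of 7,264 AD-coded pregnancies with dupilumab, 209/7,264 = 2.9%. Section 5 puts about 20% of adult AD at moderate to severe. If every user falls in that share, 209/(0.20 × 7,264) = 209/1,453 = 14.4%.

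**Simple form.** Suppose every later start comes after the loss window. Then all losses are kept and a fraction f of survivors is removed:

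- Apparent unexposed risk = 0.14/(0.14 + 0.86(1 − f)).
- Apparent RR = 0.14 divided by that risk = 1 − 0.86f.
- f = 2.9%: RR = 0.975. f = 14.4%: RR = 0.876.

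For a later entry week with remaining loss risk p, the same step gives RR = 1 − (1 − p)f. The RR therefore cannot fall below 1 − f.

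**Weekly model.** If starts also occur during the loss window, some would-be starters are lost first and remain in the comparator in proportion, which softens the effect. A discrete weekly model was run with 14% cumulative loss over Weeks 2–19, flat or front-loaded loss, entry at Week 2 or Week 8, and early, constant or late starting. The RR under no true effect was below 1 in every scenario:

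| f | RR range | Entry Week 2, front-loaded loss, constant starting: apparent unexposed risk; RR |
|---|---|---|
| 3% | 0.971–0.990 | 14.3%; 0.98 |
| 10% | 0.902–0.966 | 15.2%; 0.92 |
| 14.4% | 0.860–0.950 | 15.7%; 0.89 |
| 20% | 0.805–0.928 | 16.5%; 0.85 |

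Hazard ratios, which 7.7.3.3 specifies for this outcome, were equal or slightly lower. With unexposed status set at the entry week and no look-ahead, the unexposed risk is 14.0% and RR = HR = 1.00.

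**Combined-use exclusion.** Let s be the share of ongoing nemolizumab pregnancies that later add or switch to another study biologic (also not given). Removing them takes longer pregnancies out of the nemolizumab arm. In the simple form its apparent risk is 0.14/(1 − 0.86s), so this rule alone gives RR = 1/(1 − 0.86s), or 1.09 at s = 10%. Both rules together give (1 − 0.86f)/(1 − 0.86s), which is 1 when f = s.

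**The case against.** The best reply is that 7.3.6.1 is the detailed operating text, with a worked example, and that 7.3.6.5 is a loosely worded summary parallel to the other cohort definitions. If programmers follow 7.3.6.1, the main bias does not arise. That is fair, and it makes the bias conditional. It does not remove the contradiction: 7.3.6.5 is the section that defines this cohort, 7.1 agrees with it, and no text gives either rule precedence.

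Several stronger readings are tempting, and the protocol does not support them.

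- A reader might infer that the study will make nemolizumab look protective. The combined-use exclusion pushes the unexposed contrast towards apparent harm. The AD and PN definitions in 7.3.4 and 7.3.5 count codes and dispensings to the end of pregnancy, which makes short unexposed pregnancies harder to qualify and can also offset. The net direction is open.
- A reader might assume that 10–30% of unexposed pregnancies start later. Nothing in the protocol anchors that. Table 4 suggests about 3%, and 14.4% needs the strong assumption above. Timing relative to conception is not stated, and use before conception would lower f. Starts of nemolizumab, lebrikizumab or tralokinumab would raise it.
- A reader might treat the two-or-more-dispensings analysis as certainly biased. Section 7.7.3.5.4 does not state its entry date, and both dispensings may fall in the 95 days before conception, where no survival in pregnancy is guaranteed. The problem arises only if the first-dose entry rule of 7.3.6.1 is carried over.
- A reader might extend the figures to termination or preterm birth. The look-ahead can operate there too, but no size was worked out.

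**Conclusion.** The contradiction is explicit and needs resolving. If 7.3.6.5 governs, the rule itself is wrong for this design. With no true effect it lowers the spontaneous abortion RR to about 0.97–0.99 at f = 3% and 0.86–0.95 at f = 14.4%, so on the protocol's own counts the distortion is small to moderate. These figures assume a 14% loss risk, starting that is independent of loss, and this mechanism acting alone.

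The problem concerns secondary pregnancy outcomes in the nemolizumab-versus-unexposed contrast. The primary outcome, major congenital malformations, is analysed in live births and is largely spared. The rule does not define the active-comparator contrast.

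**What to change.** - In 7.3.6.5 and the matching bullet of 7.1, define unexposed status as no study biologic from five half-lives before conception through the end of the gestational week of cohort entry, in line with 7.3.6.1.
- State that later starters stay in the Unexposed Cohort as assigned, and add a sensitivity analysis that censors at the later start.
- Apply the combined-use exclusion in 7.3.3.2 and 7.3.6.1 only to claims up to and including the entry week.
- If the two-or-more-dispensings analysis would otherwise keep first-dose entry, start its follow-up at the second dispensing, with comparators aligned to that week.

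The cost is wording and programming, well ahead of the data extraction planned for December 2032 (Section 4). The downside is that some later-exposed pregnancies remain in the unexposed arm and dilute that contrast. Dilution grows with the share who start later and can itself mask harm, which is why the censoring analysis should accompany the main one.
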